## 8 Study Intervention

The treatment group (n=40) will be exposed to the Solius Photobiological System, and the control group (n=40) will receive the same procedure with only the blue/purple LEDs. The study intervention will involve an investigational UVB emitting device, The Solius Photobiologic System created by Solius. The Solius Photobiological System emits UVB to make sure subjects do not develop redness, the exposure will set for the lamp to 60% or 0.60 of the minimal erythemal dose (MED) for each individual's skin type.

As the appropriate doses are individualized to the subject, to establish the correct dose, each subject will complete a titration period of up to 5 weeks. The titration period will start with an erythemal weighted dose of 10.53 mJ/cm2 to 43.07 mJ/cm2 (depending on skin type) and increase by 26 - 36% each step until a maximum erythemal weighted dose of 34.88 mJ/cm2 – 109.33 mJ/cm2 (depending on skin type) or the subject shows a skin reaction. This dose will be the subject's dosage.

The device will have a strip of blue/purple LEDs installed inside the light towers. For users that are defined in the treatment group, both UV lamps and purple LED will turn on during the treatment. For users that are defined in the control group, they will go through the same pre-treatment workflow. However, when the user hits start treatment, only blue/purple LEDs will turn. The times that the control subjects will be in the sham operational device mode for the titration phase and 16-week treatment phase will be the same as those in the intervention UVB device mode based on skin type. According to a previous study by Solius where 43 subjects were exposed to a 0.6 MED, the stimulation of cutaneous vitamin D and subsequent increase in serum concentration of 25(OH)D from phototherapy was compared to the effect of a Recommended Daily Allowance (RDA) based dose of 600 IU vitamin D3 supplement daily for 10 weeks. Thus we will expose these individuals a 0.6 MED once per week for 16

weeks to observe the effect on 25(OH)D serum concentration. Serum 25(OH)D concentration will be monitored until 4 weeks after the intervention.

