As the appropriate doses are individualized to the subject, to establish the correct dose, each subject will complete a titration period of up to 5 weeks. The titration period will start with an erythemally weighted dose of 10.53 mJ/cm2 to 43.07 mJ/cm2 (depending on skin type) and increase by 26 – 36% each step until a maximum erythemally weighted dose of 34.88 mJ/cm2 – 109.33 mJ/cm2 (depending on skin type). If the subject shows a skin reaction i.e erythema, the dose will be reduced to 60% of the dose that caused the skin reaction/erythema.

The subject's dosage will be administered under conditions of full-body exposure except the face (males in swimming trunks or briefs and females in bikini or bra and panties) of 0.6 minimal erythemal dose (MED) once per week for 16 weeks. At each visit, the subject will report adverse events and any skin changes.

The PI will be available to the study staff member to answer any questions or concerns from potential subjects prior to consenting. We will have the blood samples drawn by trained professionals to minimize the risk of hematoma formation, bleeding, or infection at the site of needle insertion. Study staff will update subjects in a timely way on any new information that may affect their health, welfare, or decision to stay in this study. Any and all side effects reported will be recorded in the subjects' file in the study binder. Subjects will be instructed to call the study staff immediately if any side effects do occur. The PI will advise the study staff who have received the information from the subject as to how this side effect should be handled, recorded and reported. After the determination, all samples will be de-identified. We have a plan to protect subject privacy and confidentiality, which is explained in the plan to protect subject privacy and confidentiality in the data section.

Vitamin D deficiency and insufficiency is common in adults due to an inadequate dietary intake of vitamin D and or inadequate sun exposure. Chronic (years to decades) vitamin D deficiency and insufficiency can lead to bone loss resulting in increased risk of fracture later in life. Chronic vitamin D

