deficiency can also cause a mineralization defect of the skeleton resulting in osteomalacia. Short term (6 months) vitamin D deficiency and insufficiency is not associated with significant bone loss or osteomalacia. Therefore, the participants, especially those who are in the sham treatment group, are at no increased risk for fracture or osteomalacia. At the termination of this study those participants who were in the sham group will be encouraged to take a vitamin D supplement along the guidelines recommended by the Endocrine Society to correct their vitamin D deficiency and insufficiency.

Chronic excessive exposure to sunlight or ultraviolet radiation for prolonged periods of time, in years or decades, can increase risk for nonmelanoma skin cancer. To minimize the risk the subjects will be 22 years and older and will be exposed to suberythemal doses of UVB radiation for the duration of the study

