## 10.2 Safety Review

[name] or [name] will interview the subjects in the intervention and sham groups before their next exposure each week for any adverse events including erythema or any other skin reactions. At the time of the evaluation, it will be determined whether the subject will continue with the next exposure or whether the subject will be removed from the study. This will be based on the determination of the degree of erythema or adverse skin reaction.

In addition, Prior to each treatment, Solius software will prompt the user with the following questions to assess erythema:

- 1. Did you observe any pinkness (similar to sunburn) after your last treatment? (yes / no)
- 2. Did the pinkness last for more than 3 days? (yes / no)

3. Did you experience any pain or discomfort (excluding itch) with the pinkness? (none / mild / moderate/ severe)

Based on the user's response, the software could maintain current dose, reduce dose, or block account for further investigation. The PI or [name] or [name] will be notified to perform further assessment if an account was blocked by the software.

Side effect	Signs/symptoms	Instruction for subjects on
		monitoring
Sunburn	Pain, tenderness of the	Check for pain and redness 4-6
	skin, redness, tightness,	hours after treatment. If there
	itching, and rarely	is severe pain, should seek
	blistering	medical attention.
		If there are blisters, should seek
		medical attention
Photoaging	Atrophic skin, coarseness,	If there is increased fragility (i.e.
	fibrotic areas, increased	easy bruising or tearing of skin),
	fragility, laxity, mottled	then should seek medical
	pigmentation,	attention. The other
	telangiectasias, wrinkling	photoaging side effects are
		benign and more of a cosmetic
		nature.
Tanning	Skin darkening	As a benign side effect, no
		subject monitoring is needed

The following known side effects of UVB will be monitored:

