# 10.4 Stopping Rules

A subject will be withdrawn from the study if refuse to participate, or if the subject undergoes an adverse reaction to the light source e.g. skin erythema or pruritus.

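### The erythema rules conflict: Section 8 omits the reduction to 60% that Section 6.1 applies after a titration reaction, and Section 10.4 withdraws for ungraded erythema or pruritus where Sections 6.1 and 10.2 adjust the dose or judge by degree

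*Combined protocol and SAP*

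**What the plan says.** **Dose after a titration reaction.** Sections 6.1 and 8 describe the same titration, with the same starting doses, step sizes and maxima. Section 8 escalates to the maximum for the skin type "or the subject shows a skin reaction. This dose will be" the dosage. Section 6.1 says that if erythema appears, "the dose will be reduced to 60% of the dose that caused the skin reaction/erythema". Section 8 states a 0.6 MED target in the paragraph before the titration rule and again after it ("Thus we will expose these individuals a 0.6 MED once per week"). Section 6.1 adds that subjects "will be exposed to suberythemal doses of UVB radiation for the duration of the study".

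**What a reaction leads to.** Section 10.4 withdraws a subject from the study "if the subject undergoes an adverse reaction to the light source e.g. skin erythema or pruritus". It gives no grade and no exception for titration. In Section 10.2, staff interview subjects before the next exposure and "it will be determined whether the subject will continue with the next exposure" or be removed. "This will be based on the determination of the degree of erythema or adverse skin reaction". Section 10.2 also has the device ask about pinkness before each treatment, after which "the software could maintain current dose, reduce dose, or block account for further investigation". Section 6.3 requires exposure to stop at once for reactions it calls significant, and illustrates these mainly by severity.

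**The concern.** The two dose rules cannot both be followed. Section 8 is where a reader looks up the intervention, and its rule makes a dose that has already caused a skin reaction the weekly dose for 16 weeks. That is a safety problem in a protocol whose stated aim is to stay below the erythema threshold.

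The withdrawal rule has a different consequence. A mildly pink subject could be withdrawn, given a lower dose or continued unchanged, depending on which section staff consult. Titration is done within the allocated arm (Section 2), so these exits come after randomisation. Sham subjects can report itch or pinkness too, but erythema caused by UVB should appear mainly in the UVB arm. A literal Section 10.4 could therefore remove outcomes unevenly from a comparison that Section 12 analyses by intention to treat.

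**Working it through.** **1. Is it one ladder?** The inputs, given identically in Sections 6.1 and 8, are a start of 10.53 to 43.07 mJ/cm2, a maximum of 34.88 to 109.33 mJ/cm2, steps of 26 to 36%, and up to 5 weeks. Five weekly doses make four increments, so step = (maximum/start)^(1/4) − 1. I pair the low ends together and the high ends together, which is an assumption.
- Low end: 34.88/10.53 = 3.312, and 3.312^(1/4) − 1 = 34.9%.
- High end: 109.33/43.07 = 2.538, and 2.538^(1/4) − 1 = 26.2%.

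Both fall within the stated 26 to 36%. The ladder is coherent, and the two sections differ only in what follows a reaction.

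**2. Size of the dose conflict.** Let D be the dose that caused the reaction. Section 8 gives 1.00 × D and Section 6.1 gives 0.60 × D, a cut of 40%. The ratio is 1/0.60 = 1.67. If the reaction occurs at the maximum:
- low end: 34.88 against 0.6 × 34.88 = 20.93 mJ/cm2;
- high end: 109.33 against 0.6 × 109.33 = 65.60 mJ/cm2.

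**3. The gap in titration steps.** Suppose the reaction comes after at least one tolerated dose. Relative to the last tolerated dose:

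| Step size | Section 8 dose | Section 6.1 dose | Gap in steps |
|---|---|---|---|
| 26% | 1.26 | 0.6 × 1.26 = 0.756 | ln(1/0.6)/ln(1.26) = 2.21 |
| 36% | 1.36 | 0.6 × 1.36 = 0.816 | ln(1/0.6)/ln(1.36) = 1.66 |

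Section 8 therefore leaves the subject above the last tolerated dose, and Section 6.1 puts the subject below it.

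**4. The withdrawal rules side by side, for mild erythema.**

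| Section | Consequence |
|---|---|
| 6.1 (titration) | Dose lowered to 60% of the reacting dose; subject continues |
| 10.2 (staff review) | Continue or remove, by degree |
| 10.2 (software) | Maintain, reduce or block |
| 10.4 | Withdrawn from the study |

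Section 10.4 conflicts directly with Sections 6.1 and 10.2. It sits poorly with Section 6.3, which ties stopping to severity, but does not contradict it outright.

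**5. Do the defects combine?** If Section 10.4 is applied literally, a reactor leaves and is not dosed again. Repeated dosing at the reacting level arises only if Section 10.4 is not applied. For one subject it is one or the other.

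**6. Size of any bias.** This needs a reaction rate by arm. The documents give none, so I compute nothing.

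**The case against.** The best reply on dose is that Section 8 contains a slip and nothing more. The 0.6 MED target stands on both sides of the sentence, Section 6.1 states the reduction explicitly, dosing runs through the device's titration system and software profiles (Sections 2 and 9), and the software asks about pinkness before each session. Much of this stands. A reader might infer that reactors will in fact be treated every week at a dose that burns them. The documents do not show that, because the 1.67 measures the gap between two written rules and not a delivered dose. What remains is that the safeguards act after an exposure and leave the stated dose uncorrected.

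On withdrawal, a reader might infer that Section 6.3 allows exposure to stop for its listed reactions alone. It says neither that nor that its list is complete, so the firm conflict is with Sections 6.1 and 10.2.

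A reader might also infer a demonstrated bias or loss of power. Without a reaction rate, neither follows. Section 12 commits to intention to treat, and Section 9 requires a final sample before removal. That sample may precede Week 21, however, and the plan does not say how it enters the 16-week endpoint. Section 9 also leaves unclear whether draws continue for those who stop early.

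**Conclusion.** The point holds as a conflict between operative rules, and it should be fixed. For subjects who react during titration, Section 8 read literally sets 1.67 times the dose that Section 6.1 intends, a gap of about 1.7 to 2.2 titration steps. How many subjects this affects is not stated. The Section 8 wording is probably a drafting error, and the weekly review limits repeated exposure.

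Section 10.4, which has no grade, conflicts with the dose reduction in Section 6.1 and the degree-based review in Section 10.2. Read literally, it would remove subjects after randomisation, plausibly more often under UVB. That direction rests on UVB erythema being mainly an active-arm event, and the size of any bias is unknown. The two harms should not be added together, since they are alternatives for any one subject. Confidence is high in the textual conflict. The documents do not settle what it would do to the results.

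**What to change.** **Section 8.** Replace the sentence that fixes the dosage with: *If no skin reaction occurs, the dosage is the highest dose reached, up to the maximum for the skin type. If a reaction occurs, the dosage is 60% of the dose that caused it.* The first sentence also covers a subject who ends titration with neither a reaction nor the maximum. Confirm that the device's dosing profiles follow the same rule.

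**Section 10.4.** Replace the ungraded rule with: *Exposure stops for a significant adverse reaction (Section 6.3) or when the degree-based review in Section 10.2 so decides. Other erythema or pruritus is managed under Sections 6.1 and 10.2 (maintain or reduce the dose).* Naming both options keeps the text consistent with the software and gives mild pruritus a rule.

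**Follow-up.** Add: *Stopping exposure does not end follow-up; scheduled 25(OH)D draws continue through Week 21 unless consent is withdrawn.*

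**Cost.** This needs an amendment with IRB review and a software check. The draws are already scheduled. Keeping subjects with few exposures in follow-up may dilute the estimated effect.

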## 9 Study Procedures

We will advertise for this study at the Boston University Medical campus via email newsletters and advertisements on various TV screens. Once subjects have responded to the study flyer and contacted study staff, they will be screened over the phone to determine eligibility. This screen is anonymous and no answers will be recorded. During the preliminary anonymous screening telephone call, the subject will be asked about their medical history and inclusion/exclusion criteria. None of the answers or identifiable information will be recorded. Completion of the preliminary anonymous screening will be documented in the study binder. Once the subjects are determined to be eligible, they will be scheduled for their first visit to Boston University Medical Center's General Clinical Research Unit at [name] or in the clinical research space in the Vitamin D, Skin, and Bone Research Laboratory located at [name]. The study coordinator or IRB-approved research assistants will consent the subjects. [name] will not participate in consenting the subjects, but will be available to answer any questions or concerns that the subjects may have during the process. We will ask the subjects to read and ask any questions in regards to the screening process that they have prior to signing the consent form. This consent form will also allow us to perform a 25(OH)D blood screen, collect urine samples, and conduct our study experiment. Researchers will document that consent was given in our consent form log sheet where (s)he will need to sign and date that informed consent was given and that the subject received a copy of the ICF.

We plan to use sham control with doing a modification on instrument hardware and software. The research coordinator will be responsible for randomization and allocation. Thus, the study will be blinded to other members of the research team. Approximately 100 adult subjects with 5 skin types groups (I, II, III, IV and V/VI) will be enrolled for vitamin D deficiency/insufficiency screening. We expect at least 80% of the population in the Boston area has a level of 25(OH)D below 30 ng/ml. Thus, we will enroll approximately 100 subjects with different group skin types to enroll 80 vitamin D deficient or insufficient subjects in this study. They will be randomized to receive or not to receive the UVB intervention (40 subjects in the treatment group and 40 subjects in the control group) (Figure 1). The device will have a strip of colored LED installed inside the light towers. For users that are defined in the treatment group, both UV lamps and colored LED will turn on during the treatment. For users that are defined in the control group, they will go through the same pre-treatment workflow. However, when the user hits start treatment, only blue/purple LEDs will turn on instead of the UV lamps, which are invisible. To elaborate further, all subjects will use the same device with the exact same workflow on the touchscreen user interface. The experience in starting a SOLIUS session, answering the safety questions, automatic dispensing of eyewear, etc. will be exactly the same for active and control subjects. This is achieved by adding an independent software branch to the existing system that replicates the user workflow code but only turn on the LED drivers. LED strips are added to the existing light tower, and the lights will project through the same light path as the UV lamps. As a result, visible blue/purple light will be emitted from the same emitting window as the UV lamps. The subjects will not know if they are being actively treated or not and we will make the experience for both be virtually the same. The research coordinator who sets up the device will know only which arm the subject is assigned to (arm A or B) but will not know which arm is the treatment or control.

Blood samples that will be obtained from all participants at the screening visit will be sent to either BMC's clinical laboratory or a local Quest laboratory for a 24 hour turnaround to determine eligibility of each participant. All blood samples collected monthly during the intervention and weekly after the intervention will be sent to Quest Diagnostics for measurement of serum concentrations of 25(OH)D by liquid chromatography with tandem mass spectrometry analysis. The study design is summarized in Figure 1 and Table 2. As shown in the Table 2, blood samples will be collected at the screening visit, during the intervention period (week 1, week 5, week 9, week 13, week 17, week 21) and after the intervention (week 22 – 25). We will collect an additional tube of blood for future study at week 1, week 5, week 13, week 21 and week 25.

Each subject will be advised to come in for five titration visits. The purpose of these visits to establish the correct UVB dose in the SoliusONE device or to expose the control group for this same amount of time in the sham operated device for their skin type. At these visits, each subject will be asked questions about consumption of vitamin D, sun exposure, and whether he/she has had any adverse changes in his/her health. After the titration visit, each subject will complete a 16-week course of SoliusONE treatment or sham treatment. During each titration/treatment session, the study personnel will record subject's information in the application that is installed in the study personnel's smartphone. The information to be recorded include subject ID, age and sex. This allows the software to link to database and create user profiles for dosing. None of the identifiable information will be recorded in the application. Then, each subject will stand in the SoliusONE device while exposed to UVB light or LED visible blue/purple light. Each subject will be asked to wear a swimsuit, swimming trunks (for males) or bikini (for females) while being exposed to UVB or sham LED light in the device. The device is large enough so that the participant is able to remove their clothing and to hang it up on a hook that is provided in the device. If they are wearing their bathing suit, they will then be exposed to the UVB radiation and blue/purple light or the sham group will be exposed to only the blue/purple light . If they have brought their bathing suit with them, they will be able to put it on in the device and then be exposed to the UVB light. They then have the option of keeping the bathing suit on and dressing or removing the bathing suit and putting on all of their undergarments and clothing before exiting the device. For those who either do not want to wear a bathing suit under their clothing or have forgot to bring their bathing suit then they will have the option of being exposed to the UVB in their underwear (males in their underwear shorts and females in their panties and bra). Each session will take approximately 2-10 minutes depending on the subject's skin type group (lighter skin type groups require less treatment time). Before and after each treatment, the device will be cleaned using disinfectant to ensure proper hygiene.

Blood samples will be obtained from all subjects (cases and controls) at the screening visit and monthly throughout the 16 weeks of the study duration (weeks 1, 5, 9, 13, 17, 21), and weekly after the 16-week intervention for 4 weeks (week 22 - 25). Blood samples will be sent to Quest Diagnostics for determining the serum 25(OH)D levels. The study design summarized in Figure 1 and Table 2

If a subject needs to end his/her regiment early they will be able to do so, with no change to the study procedure. We will require a final blood sample collection from the study subject prior to his/her removal.

We anticipate the entire study will take 12 months to complete 16-week treatment for case group. As discussed earlier the study subject's involvement will last 26 weeks from screening to completion include one week for screening, 5 weeks for titration, 16 weeks for treatment and 4 weeks of post-treatment serum 25(OH)D monitoring.

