# 12 Statistical Plan

The endpoint is the difference in vitamin D insufficiency/sufficiency prevalence between the treatment and the control group use at 16 weeks of follow-up. The subject will have at least one serum 25(OH)D

evaluation within 16 weeks, and at least one phototherapy session in the 16 weeks follow up. The protocol includes a sample size calculation, which allowed for a loss to follow-up of 15%.

Statistical analysis will be performed using SPSS Statistics, version 25 (IBM Corporation). Age, sex, BMI, and Fitzpatrick skin type will be matched in two study groups. Two-sided P < .05 will be considered significant. All models will be developed according to the intention-to-treat principle. A supportive analysis will also be conducted on the per-protocol (PP) population.

The biological and clinical characteristics at enrolment will be presented, and all variables for the participants in the treatment and control groups will be compared at each follow-up using Fisher's exact test for categorical variables and a Mann–Whitney *U* test for continuous variables. For intergroup differences, 95% CIs will be also calculated. The endpoint, the proportion of subjects converting from vitamin D deficiency/insufficiency to vitamin D insufficiency/sufficiency at 16 weeks will be compared between groups using Fisher's exact test and logistic regression adjusting for skin types. Secondary analysis will be involved a comparison of changing in serum levels of 25(OH)D between groups using a Mann–Whitney *U* test and linear regression adjusting for skin types. A linear mixed model will be used to examine the relationship between phototherapy and serum 25(OH)D3 at different time points, adjusting for the baseline values and correlation of outcomes within individuals and season.

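### The stopping text does not secure a Week 21 25(OH)D value for a subject who stops exposure early, although conversion at 16 weeks is to be analysed by intention-to-treat

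*Combined protocol and SAP*

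**What the plan says.** Section 9 allows early stopping: "If a subject needs to end his/her regiment early they will be able to do so, with no change to the study procedure". The next sentence adds: "We will require a final blood sample collection from the study subject prior to his/her removal". The same section schedules blood samples for all subjects "monthly throughout the 16 weeks of the study duration (weeks 1, 5, 9, 13, 17, 21), and weekly after the 16-week intervention for 4 weeks" (Weeks 22-25). Week 21 is the end of treatment: five titration weeks plus 16.

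Section 10.2 describes the weekly review before each exposure: "it will be determined whether the subject will continue with the next exposure or whether the subject will be removed from the study". Section 10.4 states: "A subject will be withdrawn from the study if refuse to participate, or if the subject undergoes an adverse reaction to the light source", and gives erythema and pruritus as examples.

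Other passages do not mention removal. Section 6.1 reduces the dose after a skin reaction in titration. Section 10.2 also lets the device software keep the dose, reduce it, or block the account pending assessment. Section 6.3 says that the intervention stops at once after a significant adverse reaction, and does not mention leaving the study.

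In Section 12, conversion "at 16 weeks will be compared between groups using Fisher's exact test and logistic regression adjusting for skin types". On the principle: "All models will be developed according to the intention-to-treat principle". Each subject is to have at least one 25(OH)D "evaluation within 16 weeks, and at least one phototherapy session in the 16 weeks follow up". No rule is given for a subject whose 16-week status is unknown.

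**The concern.** Read together, Sections 9, 10.2 and 10.4 most naturally treat the end of exposure as the end of participation, with one last sample on whatever day that happens. An intention-to-treat comparison of status at 16 weeks needs the Week 21 value of everyone randomised, on exposure or not. If the sample is never drawn, no analysis can recover it. The analyst would have to use a value taken partway up a curve that the plan expects to rise, or treat the subject as missing.

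The loss may also be related to treatment. Section 6.1 lists erythema as a main acute effect of UVB, the sham emits visible light only, and Section 10.4 names erythema as a ground for withdrawal. Randomisation does not protect against loss of that kind. The linear mixed model in Section 12 can use partial series, but it addresses 25(OH)D levels. The conversion endpoint rests on Fisher's exact test and logistic regression.

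This is a question of which visits take place, not of who belongs in the analysis set. It also affects a subject who has had many sessions and several samples.

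**Working it through.** **Inputs.** 40 per arm; conversion 70% (UVB) and 30% (sham); gain 10 ng/mL, SD 5, linear, at least 2.5 per four weeks (all Section 12.2). Loss to follow-up 15% (Section 12).

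**The plan's own figure.** With the rounded z-values of Section 12.2: N = (2.58 × √0.5 + 0.84 × √0.42)² / 0.4² = (1.824 + 0.544)² / 0.16 = 35.07. The stated 35 per arm reproduces.

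**How many are affected, at most.** 0.15 × 40 = 6 per arm, leaving 34 with a Week 21 value, one short of 35. This is a ceiling, because the 15% also covers refusals and lost contacts.

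**If the removal-day sample is used.** Assumptions: normal gains, SD 5 at every visit, and one required gain g for all subjects. In reality g depends on each subject's baseline.

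- Find g such that P(gain > g) = 0.70 when the mean gain is 10: g = 10 − 0.524 × 5 = 7.38 ng/mL.
- The probability of conversion at an earlier mean gain m is P = 1 − Φ((7.38 − m)/5).
- The UVB arm rate with 6 such subjects is (34 × 0.70 + 6 × P)/40.

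The plan does not fix when the rise begins. Section 12.2 ties the +10 to the 16 intervention weeks (from Week 5), but the schedule has exposure from Week 1. Both clocks are shown.

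| Removal at | m from Week 5 | P | Arm rate | m from Week 1 | P | Arm rate |
|---|---|---|---|---|---|---|
| Week 9 | 2.5 | 16% | 62% | 4 | 25% | 63% |
| Week 13 | 5.0 | 32% | 64% | 6 | 39% | 65% |
| Week 17 | 7.5 | 51% | 67% | 8 | 55% | 68% |

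The UVB arm would show about 62-68% instead of 70%. The 70% is the rate under full treatment. A stopper's true off-exposure status at Week 21 is unknown and could be above or below the removal-day status.

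**If the 6 are missing.** Take 24 of 34 observed converters in the UVB arm (about 70%) and 10 of 34 in the sham arm (about 30%). The UVB rate then lies between 24/40 = 60% and 30/40 = 75%, and the sham rate between 10/40 = 25% and 16/40 = 40%.

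| Handling of 6 missing per arm | UVB | Sham | Fisher p |
|---|---|---|---|
| Observed cases only | 24/34 | 10/34 | 0.0014 |
| Missing = not converted | 24/40 | 10/40 | 0.0030 |
| All against treatment | 24/40 | 16/40 | 0.117 |
| All for treatment | 30/40 | 10/40 | 0.00001 |

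The last two rows are extreme bounds, not forecasts.

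**The case against.** The strongest reply is that "If a subject needs to end his/her regiment early they will be able to do so, with no change to the study procedure", together with sampling of all subjects, means that visits continue and that the final sample applies only to someone who then leaves. That reading is possible. But the next sentence speaks of removal, Sections 10.2 and 10.4 use the same language, and nothing states that a subject who has stopped exposure keeps the Week 21 draw. The ambiguity stands, and only a protocol edit settles it.

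Three stronger readings are tempting, and the documents do not support them.

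- *Nobody who stops early will have an end-of-treatment value.* This is too absolute, because the wording on an unchanged procedure points the other way, and Section 6.3 stops the intervention without mentioning removal.
- *Losses will fall mainly in the UVB arm.* This requires Section 10.4 to be applied to any erythema. Sections 6.1 and 10.2 describe dose reduction, under which such subjects stay on exposure, and Sections 6.1 and 8 plan 0.6 MED to avoid redness. No rate by arm or cause is given.
- *The 10-15% in Section 12.2 is the dropout rate.* That figure combines screen failure with dropout. The 15% in Section 12 is loss to follow-up, but not all of it is early stopping.

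It can also be said that a removal-day value mostly lowers the UVB rate, so any error is conservative for the device. That is broadly so against full treatment, but it is not assured for off-exposure status at Week 21. In the military study in Section 3.1 the phototherapy median was 30.0 ng/mL at month three and 27.0 at four months. A level once reached may therefore not hold.

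Finally, Section 12's requirement of one 25(OH)D value within 16 weeks may define who is analysed. It does not say that an earlier value replaces the 16-week one.

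**Conclusion.** The concern holds in a limited form. The stopping passages read most naturally as removal from the study when exposure ends, but they do not agree with each other and must be reconciled. As written, they secure no Week 21 value for a subject who stops early, and the analysis section supplies no rule for that gap.

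At the ceiling of 6 per arm, removal-day values would put the UVB rate at about 62-68% instead of 70%, and missing values would leave it between 60% and 75%. The first range rests on normal gains with constant SD 5, a single required gain and a linear rise. The second rests on 24 of 34 observed converters. The expected result survives counting missing as not converted (p = 0.0030). Only the extreme allocation against treatment removes significance. Loss related to arm is plausible but not established.

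This should be fixed before enrolment: it bears on the conversion endpoint, and a sample not drawn is lost for good. It does not show that the trial would fail or that its result would favour the device.

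**What to change.** **Sections 9, 10.2 and 10.4.** Define stopping exposure and leaving the study as separate events, and reconcile these sections with Sections 6.1 and 6.3. The reasons for stopping and the dose rules are for the sponsor and investigator to settle; this point proposes no change to them. In both arms, a subject who stops exposure and does not withdraw consent stays on the already scheduled 25(OH)D draws and adverse-event visits, at minimum Week 21.

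**Section 12.** State that:

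- the Week 21 value determines the intention-to-treat conversion endpoint whether or not exposure continued;
- a removal-day sample does not stand in for it;
- a missing Week 21 status is counted as not converted, with a sensitivity analysis under other assumptions.

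**Cost.** Protocol and consent wording, plus blood-only visits for a few subjects at dates already scheduled and paid per visit. Some stopped subjects will not return, so the missing-status rule is still needed. Section 6.2 advises vitamin D supplements. Any supplement started after stopping exposure can affect the Week 21 value and must be recorded.
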